### **2.3.2.1 Sensitivity Analysis**

Sensitivity analysis will be performed on the successfully implanted population using multiple imputation (MI).

The multiple imputation model is specified in Appendix B.

### **2.4 Sample Size Calculations**

Data on a minimum of [REDACTED] attempted subjects will be included in order to have [REDACTED] evaluable subjects in the registry.

## Statistical Analysis Plan

### 2.4.1 Primary Safety Endpoint

The assumed SADE rate is based on the LBBAP data in the literature. According to data from [REDACTED], the overall incidence rate of LBBAP lead-related complications was [REDACTED]

Assuming:

- [REDACTED] freedom from LBBAP lead-related SADEs (i.e., assumed SADE rate of [REDACTED])
- [REDACTED] power
- Binomial exact test
- One-sided alpha of 0.025
- Performance goal of 81.2%
- [REDACTED] attrition

The minimum sample size to reject the null hypothesis is [REDACTED] evaluable patients. We assume [REDACTED] attrition as subjects must have data through 6 months to qualify for enrollment in the study, so the study sample size of [REDACTED] subjects will be sufficient to evaluate the primary safety endpoint. Evaluable subjects are defined in Section 2.3.1.

The sample size calculation was performed using the PASS 15 Tests for One Proportion module.

### 2.4.2 Primary Effectiveness Endpoint

The assumed success rate is based on the LBBAP data in the literature. Given the lack of individual patient-level data for electrical performance, the overall implant success rate is used as a proxy to evaluate the composite success rate of acceptable capture thresholds and sense amplitudes for LBBAP through 6 months post-implant. According to the meta-analysis of 10 LBBAP studies, the overall range of LBBAP implant success rate with consideration of LBBAP electrical performance was [REDACTED] with [REDACTED] of success rate from meta-analysis.

Assuming:

- A composite success rate of [REDACTED]
- [REDACTED] power
- Binomial exact test
- One-sided alpha of 0.025
- Performance goal of 80%

The minimum sample size to reject the null hypothesis is [REDACTED] evaluable patients. Assuming approximately [REDACTED] of subjects will not have a successful LBBAP implant per protocol, and that about [REDACTED] of subjects will not have evaluable capture threshold and/or sense amplitudes, [REDACTED] subjects will be enrolled to ensure that [REDACTED] subjects are evaluable for the primary effectiveness endpoint. Evaluable subjects are defined in Section 2.3.2.

The sample size calculation was performed using the PASS 15 Tests for One Proportion module.

## Statistical Analysis Plan

### 2.5 Interim Analysis

No formal interim analyses are planned for this study. As such, no formal statistical rule for early termination of the trial is defined. Interim study reports with descriptive analysis may be produced for regulatory or reimbursement purposes.

### 2.6 Timing of Analysis

The Sponsor will conduct the primary endpoint analyses when required data collection is complete.

### 2.7 Study/Trial Success

Success will be declared if both the Primary Safety Endpoint and Primary Effectiveness endpoints are met.

### 2.8 Subgroups for Analysis

Abbott will also conduct subgroup analyses to estimate the effect of the implanting physician's experience with LBBAP implantation on the primary endpoints. Implanters will be classified as more-experienced or less-experienced based on the number of LBBAP implants they have performed with the Tendril STS 2088 lead. As sites are instructed to enter data consecutively from their first 2088 attempt, implant experience can be derived by ordering implant and implant date. We will consider implanters less-experienced with less than 6 implant attempts and more-experienced after they have completed 6 or more implant attempts.

As some subjects will be implanted with non-Abbott, market-approved pacemaker, defibrillator, and/or CRT devices used in combination with the Tendril 2088 lead, another subgroup analysis will be performed to determine the effect of manufacturer on the primary endpoints. In this analysis, subjects implanted with non-Abbott devices will be compared to subjects implanted with Abbott devices.

Other subgroup analyses may be performed on an ad hoc basis to understand outcomes for specific indications and patient populations.

### 2.9 Handling of Missing Data

The primary safety endpoint analysis will include evaluable subjects only. The primary effectiveness endpoint analysis will use [REDACTED]

[REDACTED] All other outcome measures will be based on the available data, with no imputation for missing values.

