## Clinical Investigation Plan

Data included in this LBBAP data collection registry will be from subjects followed for 6 months ( $\pm$  3 months) after attempted implant of LBBAP location. Data will be collected from previously occurring visits at pre-implant (baseline, required), implant (required), 6 months ( $\pm$ 3 months, required), and 12 months (- 2, +4months, optional).

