## Clinical Investigation Plan

### 6.2 Schedule of Events

CIP Activity	Baseline (≤ 3 months prior to an attempted implant of LBBAP, required)	Implant Attempt (required)	6 Month (±3 months post-attempt, required)*	12 Month (-2, +4 months post- attempt, optional)*
Data transfer notification/Informed consent process (if required by EC/IRB)	X			
Demographics (if provided)	X			
CV history and other significant medical conditions	X			
Implant indication	X			
Cardiac Medications	X			
QRS duration and QRS morphology** (if available)	X	X	X	X
NYHA classification (if available)	X		X	X
LVEF, LVEDV, LVESV (if available)	X	X	X	X
12-lead ECGs (if available)		X		
Post-implantation fluoroscopic images in any views (if available)		X		
Implanted device Information		X		
Number of LBBAP lead repositioning attempts and reason(s) for repositioning		X		
Procedure/fluoroscopy times/radiation dose		X		
Implant tools information		X		
LBBAP capture threshold, pulse width, sense amplitude, lead impedance		X	X	X
Adverse Event		(X)	(X)	(X)
Death	(X)	(X)	(X)	(X)
Product Out of Service		(X)	(X)	(X)
System Revision		(X)	(X)	(X)

(x) if applicable

\* If there are multiple visits within the visit window, the closest visit to 6 and 12 months will be captured using the scheduled follow-up CRF and other visit(s) will be captured using the unscheduled follow-up CRF.

\*\* Intrinsic QRS morphology is only applicable at baseline

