### 2.2 Statistical Methods

#### 2.2.1 Descriptive Statistics for Continuous Variables

For continuous variables (e.g., age), results will be summarized with the numbers of observations, means, and standard deviations, with quartiles, minimums, maximums, and 95% confidence intervals for the means as per the table mockups.

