## Statistical Analysis Plan

- Implant success or failure for an LBBAP lead and if not successful, reasons for unsuccessful implant
- Number of repositioning attempts at implant
- Overall procedure time: skin-to-skin
- Implant procedure time: vascular access to lead fixation
- Fluoroscopy time and radiation dose
- Implant tools used (i.e., catheter, stylet, etc.): manufacturer, model#
- Mortality

These data points will be reported for the Implanted Population:

- Capture threshold, pulse width, sense amplitude, and pacing impedance at all follow-up visits
- QRS duration and morphology (if available)
- NYHA classification (if available)
- LVEF, LVEDV, LVESV (if available)

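### Serial lead and cardiac-function measures are summarised visit by visit on available data with no within-subject change, so differences between visits can reflect who was measured

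*SAP*

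**What the plan says.** SAP 2.9 (Handling of Missing Data) covers everything outside the primary endpoints in one sentence: "All other outcome measures will be based on the available data, with no imputation for missing values". Protocol 8.6 has the same rule, so the redaction elsewhere in SAP 2.9 does not hide it. Multiple imputation (SAP 2.3.2.1 and 2.12) is planned for the primary effectiveness endpoint only.

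For the implanted population, SAP 3.5 lists "Capture threshold, pulse width, sense amplitude, and pacing impedance at all follow-up visits", followed by QRS duration and morphology, NYHA class, and LVEF with ventricular volumes, these last three groups only where available. Under SAP 2.2.1, for continuous variables, "results will be summarized with the numbers of observations, means, and standard deviations", with quartiles, range and 95% confidence intervals for the means as the table mockups require. SAP 2.2.2 gives counts and percentages for categorical variables.

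Coverage differs by visit. Protocol 3.1 and the schedule in Protocol 6.2 make baseline, implant and 6 months (±3) required and 12 months (−2, +4) optional. Lead readings start at implant. NYHA is scheduled at baseline, 6 and 12 months. QRS and LVEF with volumes are scheduled at all four time points, always subject to availability. Where several visits fall in one window, the closest to the target goes on the scheduled form and "other visit(s) will be captured using the unscheduled follow-up CRF".

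SAP 3.5 states that these items are descriptive and that no hypothesis tests will be performed.

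**The concern.** The registry is meant to support an indication expansion (Protocol 1.0), and Protocol 1.1.1 refers both to stable lead parameters under LBBAP and to left ventricular dysfunction with right ventricular pacing. Readers will therefore compare threshold and LVEF summaries across visits. In a chart review, whether a patient has a repeat echocardiogram or a recorded 12-month device check depends on local practice and may depend on the patient's condition. If it does, and to a different degree at different visits, two visit columns describe different sets of patients. The difference between their means then mixes real change with a change in who was measured. The reported number of observations shows that patients are missing, but not which ones.

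What is at stake is the description of electrical stability after 6 months and of cardiac function over follow-up, not a formal test.

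**Working it through.** The documents give no figure for these visit summaries, so there is nothing of the plan's own to reproduce. The check asks how far an available-data summary can move when no patient changes. All patient mixes and measurement probabilities below are assumptions.

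**General form.** Let a fraction f be measured at the later visit, and let d be the mean of measured minus unmeasured subjects. The full mean is f × M(measured) + (1 − f) × M(unmeasured), so

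apparent shift = M(measured) − M(all) = (1 − f) × d.

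With f from 30% to 90% and d from 0.2 to 0.5 SD:

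- smallest: (1 − 0.9) × 0.2 = 0.02 SD
- middle: (1 − 0.5) × 0.3 = 0.15 SD
- largest: (1 − 0.3) × 0.5 = 0.35 SD

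If 190 subjects (the evaluable number in Protocol 8.3.2) are measured at the first visit, the standard error of the later mean at f = 50% is 1/√95 = 0.10 SD. The middle shift of 0.15 SD therefore exceeds it.

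**Capture threshold, 6 to 12 months.** Assume 10% of leads at 2.5 V and 90% at 0.8 V. The full mean is 0.1 × 2.5 + 0.9 × 0.8 = 0.97 V. With q the probability of a 12-month reading in each group,

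observed mean = (0.1 × q_high × 2.5 + 0.9 × q_norm × 0.8) / (0.1 × q_high + 0.9 × q_norm).

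| q_high | q_norm | Calculation | Observed 12-month mean |
|---|---|---|---|
| 0.9 | 0.4 | 0.513 / 0.45 | 1.14 V |
| 0.4 | 0.4 | 0.388 / 0.40 | 0.97 V |
| 0.3 | 0.6 | 0.507 / 0.57 | 0.89 V |

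**LVEF, baseline to follow-up.** Assume 30% of subjects at 35% and 70% at 58%. The full mean is 0.3 × 35 + 0.7 × 58 = 51.1%. With f the probability of an LVEF value in each group,

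observed mean = (0.3 × f_low × 35 + 0.7 × f_norm × 58) / (0.3 × f_low + 0.7 × f_norm).

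| f_low | f_norm | Calculation | Observed mean | Apparent fall if baseline is complete |
|---|---|---|---|---|
| 0.80 | 0.25 | 18.55 / 0.415 | 44.7% | 6.4 points |
| 0.70 | 0.40 | 23.59 / 0.49 | 48.1% | 3.0 points |
| 0.60 | 0.50 | 26.60 / 0.53 | 50.2% | 0.9 points |

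Baseline LVEF is itself recorded only if available (Protocol 6.1.1), so a complete baseline is the extreme case. If the 0.80/0.25 pattern applies at both visits, both means are 44.7% and the apparent change is 0. If baseline follows 0.70/0.40 and follow-up 0.80/0.25, the apparent fall is 48.1 − 44.7 = 3.4 points. The artefact depends on the difference in selection between visits.

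**Paired change.** In all these scenarios no subject changes, so the mean within-subject change among subjects with both values is exactly 0, whatever the measurement probabilities.

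**The case against.** The strongest reply is that these endpoints are descriptive, no claim of change, stability or improvement is planned from them, and available-data summaries with the number of observations are ordinary for a chart review. SAP 2.7 rests success on the two primary endpoints alone. All of this stands. It sets the weight of the point but does not remove it, because the listed outputs will still be read across visits.

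Other limits also stand. SAP 2.2.1 and 2.2.2 defer to table mockups that are not in the documents, so a paired table there cannot be excluded. The documents do not say why a measurement would be missing; selection by clinical need is plausible but assumed.

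A reader might infer more than the documents support:

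- **That every visit column holds different patients.** For lead measurements this goes too far. Implant and 6-month visits are required, and records through 6 months (±3) are an entry condition (Protocol 5.3.2.1). Up to 6 months only item-level gaps remain; SAP 2.4.2 expects some.
- **That LVEF would falsely fall by about 6 points.** That needs a complete baseline and strongly selective follow-up. Equal selection at both visits gives 0.
- **That the share of leads at or below 2.0 V could appear to drop to the 80% goal at 12 months.** That share belongs to the primary effectiveness criterion; no 12-month responder share is listed.
- **That these tables are the only evidence after 6 months.** Adverse events, system revisions and product out of service are also collected at 12 months (Protocol 6.2). Only the electrical values lack another source.
- **That unscheduled readings will be pooled with scheduled ones.** The separate form suggests otherwise. SAP 3.5 simply does not say.

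**Conclusion.** The point holds as a limited one about describing change. On the visible text, serial measures are summarised on available data at each visit without a within-subject comparison. Differences between visit summaries can therefore reflect who was measured, if selection differs between visits. This applies to LVEF and volumes, NYHA and QRS wherever they are collected, and to lead measurements mainly at 12 months.

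Size and direction cannot be derived from the documents. Under the assumed mixes, with no true change, mean threshold moves from 0.97 V to between 0.89 and 1.14 V, and mean LVEF by 0 to about 6 points. QRS has a further problem: baseline QRS is intrinsic (Protocol 6.1.1) and follow-up QRS is paced (Protocol 6.1.3), so that comparison mixes two kinds of measurement even in the same patients.

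A reader might infer that the primary results are undermined. They are not: the primary endpoints, sample size and study success are unaffected.

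**What to change.** In SAP 3.5:

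1. Add within-subject change in subjects with both values, with the number of pairs and a confidence interval. Do this for capture threshold, sense amplitude and impedance (implant to 6 months, and 6 to 12 months) and for LVEF, volumes and NYHA (baseline to 6 and to 12 months). Base any statement of stability or improvement on these results.
2. Show earlier-visit values side by side for subjects with and without the later measurement.
3. For QRS duration, compare paced with paced (implant to follow-up, where available), and label any comparison with baseline as intrinsic-to-paced.
4. State that unscheduled-visit readings stay out of the scheduled-visit summaries.

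The available-data rule in SAP 2.9 can remain. If the mockups already contain paired tables, SAP 3.5 should say so.

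The cost is a few tables from data already collected. The paired sets are smaller, so intervals may be wider. Paired results also describe only the measured subjects, which is why item 2 is needed.

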#### 2.9.1 Partial Dates

Partial dates with a missing day (ex: --APR2022) will be imputed to the first of the month, 01APR2022. Dates with a missing month (ex: 25---2020) will be imputed to January (25JAN2020), and dates with a missing day and month (ex: -----2021) will be imputed to the first of the year (01JAN2021).

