### 5.3.2 Inclusion Criteria

#### 5.3.2.1 Inclusion Criteria

- 1) Subject has a de novo attempted implant of the Tendril™ STS 2088 lead in the Left Bundle Branch Area on or before January 31, 2023 and subject's medical records contain data through at least 6 months (+/- 3 months) after LBBAP implant attempt
- 2) Subject is  $\geq$  18 years of age or the legal age, whichever age is greater
- 3) For sites where the governing IRB/EC has not granted a waiver of informed consent, subject has either been informed of the nature of the clinical investigation using a privacy notice or has provided a signed written informed consent, as approved by the IRB/EC (Note: This inclusion criterion is not applicable for sites where the governing IRB/EC or applicable regulation has granted a waiver of patient consent)

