## 11.0 DATA HANDLING AND RECORD KEEPING

Sponsor and/or its affiliates will maintain documentation of the systems and procedures used in data collection for the duration of the clinical investigation.

CRF data collection will be performed through a secure web portal and only authorized personnel will access the EDC system using a unique username and password to enter, review or correct data. Passwords and electronic signatures will be strictly confidential.

The data will be subjected to consistency and validation checks within the EDC system and supplemental review by the Sponsor.

At the end of the clinical investigation, completed CRF images with the date-and-time stamped electronic audit trail indicating the user, the data entered, and any reason for change (if applicable) will be provided to the investigational sites, if requested.

For the duration of the clinical investigation, the Investigator will maintain complete and accurate documentation including, but not limited to, medical records, clinical investigation progress records, laboratory reports, CRFs, signed ICFs/data collection notifications (if applicable), device accountability

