## 2.3 Endpoint Analysis

### 2.3.1 Primary Safety Endpoint

The primary safety endpoint evaluates freedom from LBBAP lead-related SADEs through 6 months post-implant attempt.

The hypothesis is formally expressed as:

$$\begin{aligned} H_0: & \text{Freedom from LBBAP lead related SADEs} \leq 81.2\% \\ H_1: & \text{Freedom from LBBAP lead related SADEs} > 81.2\% \end{aligned}$$

The primary safety endpoint will be estimated as a binomial proportion and the 97.5% lower confidence bound (LCB) will be calculated using the Clopper-Pearson exact method. The null hypothesis is rejected at the 2.5% significance level if the LCB is greater than the performance goal (PG) of 81.2%. The p-value from a one-sided exact test for the binomial proportion will also be calculated and compared to the 0.025 significance level.

This analysis will be performed on the enrolled population, and the primary safety analysis will use evaluable subjects. Evaluable subjects will include all subjects with an implant attempt with data available for evaluation. Subjects who do not have 6 months data and do not experience a lead-related serious adverse device effect (SADE) prior to 6 months will be excluded from the analysis. Lead-related SADEs that occur through 6 months post attempted implant will be included in the primary safety endpoint analysis. No sensitivity analyses will be performed.

The primary safety endpoint performance goal derivations are provided in Appendix A.

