### 3.2 Adverse Events

All of the adverse device effects, serious adverse device effects, will be summarized for all subjects who enrolled in this trial in terms the number of events and the percentage of subjects with events.

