### 3.5 Descriptive Endpoints or Additional Data

Descriptive endpoints and additional data are reported using only summary statistics and no hypothesis tests will be performed.

These data points will be reported for the Enrolled Population:

- Demographics (if provided): sex at birth, age range
- Indication for pacemaker or CRT-P/D implant
- Cardiovascular (CV) history and other significant medical conditions
- Procedure and device-related adverse events

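### Does the partial-date rule, which has no floor at the implant attempt, put the count of early lead-related SADEs at risk?

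*SAP*

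**What the plan says.** SAP 2.9.1 gives three unconditional rules. For a missing day: "Partial dates with a missing day (ex: --APR2022) will be imputed to the first of the month, 01APR2022". A missing month becomes January, and a date with only the year becomes 1 January. Event dates get no separate treatment and the implant attempt is not mentioned.

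SAP 2.3.1 defines which events count: "Lead-related SADEs that occur through 6 months post attempted implant will be included in the primary safety endpoint analysis". Subjects without 6-month data who "do not experience a lead-related serious adverse device effect (SADE) prior to 6 months will be excluded from the analysis" are removed from the denominator. Both statements limit time from above only. The endpoint is a binomial proportion tested against 81.2% with a one-sided 97.5% Clopper-Pearson bound. No sensitivity analysis is planned for it (SAP 2.3.1 and 2.12).

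Protocol 5.3.2.1 requires that the "Subject has a de novo attempted implant", so a SADE related to the LBBAP lead cannot truly precede the attempt. Protocol 11.0 adds that "The data will be subjected to consistency and validation checks within the EDC system".

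**The concern.** Device complications cluster early, and early events are the ones an earliest-date rule pushes back past the procedure. If the analysis program read the safety window as running from the attempt to month 6 and tested both ends, an event imputed to before the attempt would fall outside it. Entry requires follow-up data at 6 months, so that subject would usually then count as event-free. The error would favour the device on a primary endpoint, and no safety sensitivity analysis would expose it. Near the decision boundary one lost event could turn a failure into a pass. Any time-to-event display measured from the attempt would also contain a negative time.

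**Working it through.** **1. The impossible date is real.** Attempt 20 April 2022, true SADE 24 April 2022. Recorded without the day, it becomes 1 April (day -19). Recorded with the year only, it becomes 1 January (day -109).

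**2. How often.** For 730 consecutive attempt dates from 1 January 2021 and every lag in the range, count the day-missing cases in which the first of the event's month precedes the attempt:
- Lags 0-30: 10,746 of 22,630 = 47.5%.
- Lags 0-183: 10,746 of 134,320 = 8.0%. The numerator is the same because no pre-attempt date arises beyond lag 30.

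**3. Does the count change under the plan as written?** The written test is: imputed date no later than 6 months (day 183). Compare it with the ideal test: some date compatible with the recorded parts lies between the attempt and day 183. For day-missing and year-only dates the two must agree. If the imputed date is on or after the attempt, it is itself a compatible date. If it is before the attempt while the true date is after, the attempt lies in the same month (or year), so the attempt date is compatible. Enumeration covered month-missing dates too: every tenth attempt date, lags 0-400 in steps of 3, three types of partial date, 3 x 9,782 = 29,346 cases. Disagreements: 0. A program with an added lower limit disagrees in 380 of the 9,782 day-missing cases.

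**4. The plan's own figure.** Protocol 8.3.1 states 165 evaluable subjects for 85% power. With n = 165 and goal 0.812, the smallest passing count is 144 event-free (exact one-sided level 0.0249). Power at a true freedom of 0.8945 is 0.850. The assumed rate is redacted; a value near 89.5% is consistent with the stated size and is used below as an assumption.

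**5. The worst case, if someone codes a lower limit.** Take n = 220, the minimum number of attempts. The lower bound is the 0.025 quantile of Beta(x, n - x + 1). With 191 event-free (29 SADEs) it is 81.62%, a pass; with 190 (30 SADEs) it is 81.11%, a fail. Let s be the share of SADE dates lacking the day (assumed 1-5%; the documents give no figure) and h the share pushed before the attempt (0.080 if events are spread over days 0-183, 0.475 if all fall on days 0-30). Each SADE is lost with probability q = s x h.

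Expected SADEs lost at 89.5% freedom = 220 x 0.105 x q = 23.1q:
- Spread: 23.1 x 0.0008 = 0.02 to 23.1 x 0.004 = 0.09.
- All early: 23.1 x 0.00475 = 0.11 to 23.1 x 0.02375 = 0.55.

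Probability of a false pass = sum over k of 30 or more of P(k SADEs) x P(at least k - 29 lost):

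| True freedom | Spread, s = 1% to 5% | All early, s = 1% to 5% |
|---|---|---|
| 92% | 0.003% to 0.017% | 0.020% to 0.089% |
| 89.5% | 0.07% to 0.32% | 0.38% to 1.8% |
| 87% | 0.18% to 0.90% | 1.1% to 5.3% |

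At a true freedom of exactly 81.2%, the chance of passing rises from 1.73% to 1.75-1.85% (spread) or 1.87-2.56% (all early). Only the most extreme combination exceeds 2.5%.

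**6. The other direction.** Of day-missing events truly on days 184-214, 47.5% are imputed to day 183 or earlier and so count as failures. As written, the rule leans against the device.

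**The case for a change.** The case for a change is that it is cheap and closes off a mistake. A sentence or two would rule out the lower-limit reading, which the SAP does not exclude, and would alter nothing for a team already using the literal one. The safeguards are also incomplete. The EDC checks name no date-order rule and act on recorded dates, before any imputation. The adverse event summaries (SAP 3.2: "All of the adverse device effects, serious adverse device effects, will be summarized for all subjects who enrolled in this trial"; SAP 3.5: "Procedure and device-related adverse events") would still show a lost event, but they are not limited to lead-related events or to 6 months.

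Those facts stand, but they do not make a defect in the primary analysis. A lower limit would have little purpose here: sites report only procedure- and device-related events and deaths (Protocol 7.3.1), and the schedule of events has no adverse event entry at baseline (Protocol 6.2), so there are no pre-attempt device events to filter out. A lead-related SADE on day -19 is visibly a date problem, and data review and discrepancy handling are assigned to a Data Management Plan (Protocol 11.2). The time-to-event worry has no definite target, since SAP 2.2.3 names no endpoint.

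The obvious remedy, taking the later of the imputed date and the attempt date, also has costs. With only the month missing, it contradicts the recorded day in 96.6% of the dates it moves (91,572 of 94,820, lags 0-183). It would also shift a date that is truly incompatible with the attempt, such as a recorded month before the procedure, to day 0 and so hide a data error that ought to be queried.

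**Conclusion.** The observation is correct: SAP 2.9.1 has no floor and can produce a date before the attempt. It does not call for a change. Under SAP 2.3.1 as written the event remains a failure and the subject stays in the denominator, so the SADE count, the bound and the verdict are unaffected. That conclusion needs no assumption about how many dates are incomplete. Harm to the endpoint requires a lower-limit test that the plan does not contain. Even with it, the false-pass probability at 89.5% freedom is at most 1.8% over the assumed 1-5% range, and reaches 5.3% only with 87% freedom, 5% partial dates and every SADE in the first 30 days together. Those sizes rest on the assumed partial-date share, the back-solved freedom rate and n = 220. What is left is a matter of presentation in listings, or in any survival display that is produced. An analyst would settle it by using the earliest date that is both compatible with the record and on or after the attempt, and by querying dates that cannot be reconciled.
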